### 4.4 Early Withdrawal of Subjects

#### 4.4.1 When and How to Withdraw Subjects

All subjects will be assessed during the 2 days of medication administration, subsequent days of medication administration, and all study visits. If a severe adverse event (SAE) occurs at any time during administration of the 2-day drug regimen, a formal review will occur, and subsequent patients will be enrolled one at a time using the same regimen. If three or more events accrue, the pilot study will be held and either a potential dosing regimen revisited, or discontinuation of the study protocol will occur. Other interventions will be at the direction of the Food and Drug Administration and Mayo Institutional Review Board.

Patients may also wish to withdraw if they perceive that their symptoms of carpal tunnel syndrome are not improving, and they wish additional treatment such as surgery or a steroid injection. If they are tolerating the Fisetin otherwise, we will request that they continue the Fisetin in addition to the other treatments, and such patients will continue to be followed, but will be excluded from the final analysis. We aim to continue enrollment until 40 patients complete the 60-day trial time point without intervening treatment for their CTS.

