## **8.3 Reporting of Serious Adverse Events and Unanticipated Problems**

When an adverse event has been identified, the study team will take appropriate action necessary to protect the study participant and then complete the Study Adverse Event Worksheet and log. The sponsor-investigator will evaluate the event and determine the necessary follow-up and reporting required.

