### 8.3.1 Sponsor-Investigator Reporting: Notifying the Mayo IRB

The sponsor-investigator will report to the Mayo IRB any UPIRTSOs and Non-UPIRTSOs according to the Mayo IRB Policy and Procedures.

Information collected on the adverse event worksheet (*and entered in the research database*):

- Subject's name
- The date the adverse event occurred
- Description of the adverse event
- Relationship of the adverse event to the research drug: Not Related, Possibly Related, Probably Related, or Related
- If the adverse event was expected
- The severity of the adverse event: (Mild, symptoms such as GI upset, nausea, or headache; Moderate, symptoms such as vomiting, vertigo, chest pain; Severe, any problem requiring more than one day of OTC medication, or requiring a doctor visit, such as chest pain, vertigo, GI bleeding, *etc*)
- If any intervention was necessary/action taken
- Resolution: was the incident resolved spontaneously or after discontinuing treatment
- Date of Resolution

The Investigator will review all adverse event reports to determine if specific reports need to be made to the IRB and FDA. The sponsor-investigator will sign and date the adverse event report when it is reviewed. For this protocol, only directly related SAEs/UPIRTSOs will be reported to the IRB. Non-UPIRTSOs/non-serious AEs will be reported at the time of annual continuing review, according to the IRB policy.

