## 8.5 Stopping Rules

All subjects will be assessed during the 2 cycles each lasting for 2 days of Fisetin administration (after Visits 1 and 2; total 4 days) and during each visit following administration of the first cycle of drugs. If a severe adverse event occurs at any time during administration of the 2-day drug regimen, the study will pause, and a formal review will occur. Subsequent subjects will only be enrolled if the SAE is determined to be unrelated to the study drug. Other interventions will be as according to the direction of the FDA and Mayo IRB.

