### Individual Subject Stopping Rules

Any subject who experiences a SAE of any sort, or who is found to meet, after enrollment, any exclusion criterion, will no longer receive the study drug.

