### Toxicity stopping rule

The study will be terminated if the number of **treatment related** deaths exceeds 0 or if SAE's in the subjects already registered and treated in the trial exceeds 3.

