### 8.6.1 Internal Data and Safety Monitoring Board

There will not be a formal DSMB. However, we will have a DSMP and the PI will monitor the progress of the study and all adverse events.

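### After a first or second drug-related, non-fatal SAE during dosing, section 4.4.1 continues enrolment and section 8.5 forbids it; nothing says which governs

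*Combined protocol and SAP*

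**What the plan says.** Section 4.4.1 (When and How to Withdraw Subjects) covers a severe adverse event, abbreviated there as SAE, at any time during a 2-day course. Its consequence is that "a formal review will occur, and subsequent patients will be enrolled one at a time using the same regimen". No attribution test is attached. Only when three or more events have accrued is the study held, with the regimen then reconsidered or the study discontinued.

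Section 8.5 (Stopping Rules) uses the same trigger but pauses the study at once, requires a formal review, and adds a condition: "Subsequent subjects will only be enrolled if the SAE is determined to be unrelated to the study drug". It does not mention enrolling one at a time.

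The Toxicity stopping rule, also in 8.5, terminates the study on any treatment-related death, or if the number of SAEs "in the subjects already registered and treated in the trial exceeds 3".

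On who decides, section 8.3 states: "The sponsor-investigator will evaluate the event and determine the necessary follow-up and reporting required". Section 8.6.1 states: "There will not be a formal DSMB". It leaves monitoring to the principal investigator under a data and safety monitoring plan.

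**The concern.** A stopping rule is useful only if it is settled before the event it governs. Here the same event leads to opposite instructions on whether a new subject may be given a regimen that has just been judged to have caused an SAE. The sponsor-investigator evaluates the event and would also have to choose, afterwards, between a looser and a stricter rule, both of which are current protocol text. The stake is the safety of subjects not yet enrolled. The affected subject is not in question, because the Individual Subject Stopping Rules withdraw study drug after any SAE.

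**Working it through.** No sample-size or power figure bears on this point, so the check is a comparison of the two rules, case by case, for an SAE during a dosing course.

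| Case | Section 4.4.1 | Section 8.5 | Can both be followed? |
|---|---|---|---|
| First or second event, judged unrelated | Review, then enrol singly | Pause, review, may resume | Yes: pause, review, resume singly |
| First or second event, judged related, non-fatal | Review, then enrol singly on the same regimen | Pause, review, no further enrolment | **No** |
| Third event | Hold the study | Pause and review | Yes: both stop enrolment at that point |
| Treatment-related death | Not addressed | Terminate (toxicity rule) | Yes: termination governs |
| More than 3 SAEs, i.e. the fourth | Study already held if all occurred during dosing | Terminate (toxicity rule) | Yes: termination governs |

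Only the second row conflicts. It presumes that the trial's total SAE count is still 3 or fewer, because the toxicity rule counts SAEs in all treated subjects and not only those during dosing.

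Next, does any text settle that row?

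- **FDA and IRB direction.** Both sections end by referring to these bodies, but only for other interventions. Neither sentence ranks 4.4.1 against 8.5.
- **Toxicity stopping rule.** Its limits are more than 0 treatment-related deaths or more than 3 SAEs. One or two related, non-fatal SAEs reach neither limit.
- **The formal review in 4.4.1.** It is given no stated power to stop enrolment after one event. The hold at three events presupposes that enrolment went on after the first and second.
- **Sections 8.3 and 8.6.1.** They say who evaluates and monitors events, not which rule applies.

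Last, what counts as unrelated? Section 8.3.1 records "Relationship of the adverse event to the research drug: Not Related, Possibly Related, Probably Related, or Related". On plain wording, Not Related satisfies the condition in 8.5. But 8.5 does not cite that worksheet scale, so the standing of Possibly Related is undefined.

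**The case against.** The best contrary reading treats the sections as complementary: 8.5 says whether enrolment may resume, and 4.4.1 says at what pace. Section 8.5 carries the Stopping Rules heading, whereas 4.4.1 concerns withdrawal of subjects and never says that enrolment continues even if the event is related. A cautious investigator would probably proceed this way. It is a sensible default, but it remains an inference, because 4.4.1 states its enrolment step without condition.

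Exposure is also bounded. Section 4.4.1 has its own brakes: formal review, single-subject enrolment and the three-event hold. There is a monitoring plan despite the absence of a DSMB. Unexpected serious suspected reactions reach the FDA within 7 or 15 days (8.3.2). Section 1.6 does not anticipate SAEs. All of this stands and limits the consequences, but none of it says which rule applies.

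A reader might infer more than the documents support:

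- **That the rules conflict for every non-fatal SAE during dosing.** They do not if the event is unrelated, nor from the third event on.
- **That they conflict for three of the four relationship grades.** That depends on a scale that 8.5 does not invoke.
- **That injection or surgery on the study wrist creates a second contradiction of equal weight.** For subjects who seek such treatment and tolerate the drug, 4.4.1 says "we will request that they continue the Fisetin in addition to the other treatments". The Individual Subject Stopping Rules say that anyone "who is found to meet, after enrollment, any exclusion criterion, will no longer receive the study drug", and 4.2.1 lists both treatments within the past 6 months as exclusions. Section 4.4.1 addresses this exact case, and the exclusion is phrased as prior history. The eligibility recheck at Day 29 (6.4) leaves some doubt, enough for a clarification and no more.
- **That the lack of a scheduled adverse event assessment on home-dosing Days 1 and 30 defeats the pause rule.** Section 8 asks subjects to contact the team immediately. A diary entry would not help, since diaries are collected at Days 29 and 60.

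**Conclusion.** The point holds as an internal inconsistency that should be fixed. For a first or second SAE during a dosing course that is judged drug-related and is not fatal, 4.4.1 and 8.5 cannot both be followed, and the protocol does not say which prevails. This rests on reading the enrolment step in 4.4.1 as unconditional, which is how it is written, and on the toxicity rule not already having ended the study.

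No number of exposed subjects can be given. The documents state no SAE rate, and enrolment is open-ended until 40 patients complete Day 60 without intervening treatment.

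Two wording faults in 8.5 add to the uncertainty. The trigger says *severe*, as it does in 4.4.1, yet the event is then called an SAE, which the abbreviation list defines as serious. In 8.3.1 *severe* is a severity grade that extends to a complaint needing over-the-counter treatment beyond one day. Section 8.5 also places dosing after Visits 1 and 2, although Visit 1 is screening.

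**What to change.** 1. Delete the trial-level stopping text from 4.4.1 and cross-refer to 8.5 as the single governing rule.
2. In 8.5, state the sequence: pause and formal review at the first SAE during a dosing course, then resume only if the event is judged unrelated. Say which grade or grades on the 8.3.1 scale count as unrelated. If one-at-a-time enrolment is kept, apply it on resumption.
3. If the three-event hold is kept, move it to 8.5 and count all such events regardless of attribution. It then sits coherently below the toxicity rule: hold at the third event, terminate when SAEs exceed 3.
4. In the trigger, replace *severe* with serious adverse event as defined in 8.1. Correct the visit reference to Visits 2A/2B and 3A/3B.
5. As a minor clarification, state in the Individual Subject Stopping Rules whether on-study injection or surgery on the study wrist stops study drug, so that they agree with 4.4.1.

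The cost is amendment wording. No extra patients, visits or data collection are needed.

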### Individual Subject Stopping Rules

Any subject who experiences a SAE of any sort, or who is found to meet, after enrollment, any exclusion criterion, will no longer receive the study drug.

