#### **4.2.2 Laboratory Exclusion Criteria:**

The following laboratory tests as indicated or as *per* clinical judgement:

- Bilirubin > 2.0; serum aspartate transaminase (AST) > 4 X upper limit of normal, or alanine aminotransferase (ALT) > 4 X upper limit of normal as a marker of liver disease
- Hemoglobin < 7g/dL; white blood cell count  $\leq$  2,000/mm^3 ( $\leq$  2.0 x 10^9/L) or  $\geq$  20,000/mm^3 ( $\geq$  20 x 10^9/L); platelet count  $\leq$  40,000/ $\mu$ L ( $\leq$  40 x 10^9/L); absolute neutrophil count  $\leq$  1 x 10^9/L; lymphocyte count  $<$  0.3 x 10^9/L at screening as a marker of poor nutrition
- Plasma and/or serum fasting glucose > 300 or HbA1c > 9 as a marker of poor diabetic control
- Creatinine > 2.5, cystatin c > 3 or eGFR < 25 ml/min/1.73 m^2 as a marker of advanced kidney disease,
- CRP > 10 or ESR > 25 as a marker of systemic inflammation
- Unstable (as per clinical judgement) major cardiovascular, renal, endocrine, immunological, or hepatic disorder

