#### **4.2.4 Medication Exclusion Criteria**

- Known hypersensitivity or allergy to Fisetin or other flavonoids
- Currently participating in another study using Fisetin or currently taking any flavonoid as a nutritional supplement. Note that consuming foods rich in flavonoids is NOT an exclusion, both because flavonoids are present in almost all fruits and vegetables, making such an exclusion impossible as a practical matter, and, from a scientific perspective, the amount of flavonoids in general, and Fisetin in particular, present in foods is far lower than the dose that will be administered in the trial.

- Patients currently taking medications listed in the Investigator Brochure are excluded unless medication can be safely held following the guidelines in the Investigator Brochure .
- If the patient is required to initiate any medication listed in the Investigator Brochure during the study, the PI will reassess their continued participation in the study.

**4.2.5 Behavioral Modifications** - Participants will be educated about the risk of excessive caffeine usage and nicotine usage. Namely,

- CAFFEINE: limit daily intake to no more than the equivalent of 4 cups of coffee per day or 400 milligrams of caffeine per day.
- TOBACCO/NICOTINE: limit daily intake to no more than a pack of day (20 cigarettes) or 20 mg of nicotine per day.

Alternatively, if a subject routinely uses more than these amounts they can be considered for enrollment if a behavior modification program is in place that reduces the daily usage by half.

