## **5.5 Prior and Concomitant Therapy**

Subjects may continue all treatments except for two related to CTS: steroid injection or surgery, during the first 60 days of the study. If a study participant is required to initiate any medication listed in Appendix 1 of the Investigator Brochure during the study, the PI will reassess their continued participation in the study.

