## 6.4 Visit 3A, Day 29 ( $\pm 2$ days)

Blood for safety tests will be collected either in Rochester or at another Mayo Clinic site more convenient to the research subject's home within 5 days prior to the scheduled appt on day 29. These results will be reviewed prior to the third IP dose, to confirm there are no clinically significant changes. On day 29, subjects will return to Mayo Clinic's Clinical Trial Research Unit (CTRU). Subjects will have their vital signs measured and review changes to their medical history and concomitant medications with the CTRU nurse to ensure they continue to meet inclusion/exclusion criteria. Women of child bearing potential will confirm their pregnancy status via a point of care pregnancy test. The study team will administer the hand examination including measurement of pinch and grip strength and record the information into REDCap, record adverse events, and collect the Subject Drug Diary. The subject will fill out hand/wrist pain VAS and hand/wrist interference VAS assessments and the Boston CTS (BCTQ) questionnaire in REDCap. The subject will provide a blood and urine sample for inflammation and senescence markers. Finally, the CTRU nurse will administer the third IP dose and provide the subject with IP for the following day (20 mg/kg/day).

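### Section 8.5 stops study drug for any exclusion criterion met after enrolment, but 4.2.4 and 5.5 leave cycle 2 to PI reassessment and 4.4.1 asks some such subjects to continue

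*Combined protocol and SAP*

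**What the plan says.** **The stopping rule.** Section 8.5 (Individual Subject Stopping Rules) says that a subject "who is found to meet, after enrollment, any exclusion criterion, will no longer receive the study drug". It covers every exclusion criterion and mentions no discretion.

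**Listed medicines.** Under 4.2.4, patients taking medicines named in the Investigator Brochure are "excluded unless medication can be safely held following the guidelines in the Investigator Brochure". The next bullet covers medicines started later: "If the patient is required to initiate any medication listed in the Investigator Brochure during the study, the PI will reassess their continued participation". Section 5.5 repeats this for a participant "required to initiate any medication listed in Appendix 1 of the Investigator Brochure during the study, the PI will reassess their continued participation".

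**Steroid injection or wrist surgery.** Section 4.2.1 excludes anyone who has had a carpal tunnel steroid injection, or surgery on the affected wrist, in the preceding 6 months. Section 4.4.1 considers subjects who seek those same treatments because they are not improving. If they tolerate fisetin, they are asked to keep taking it and are followed, but are left out of the final analysis.

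**Day 29 checks.** Section 6.4 says of the safety laboratory tests: "These results will be reviewed prior to the third IP dose, to confirm there are no clinically significant changes". It also has the subject review history and medicines "with the CTRU nurse to ensure they continue to meet inclusion/exclusion criteria", and Table 1 marks the eligibility row at Day 29. The laboratory limits in 4.2.2 open with: "The following laboratory tests as indicated or as *per* clinical judgement".

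**The concern.** The decision at issue is whether to re-dose a subject whose status has changed since entry. The protocol foresees the situation: the Serious Adverse Event definitions in 8.1 class a change that brings a subject within the exclusion criteria as a non-serious adverse event, but give no dosing consequence. Section 8.5 makes the decision for the site. Sections 4.2.4 and 5.5 hand it to the PI, and 4.4.1 points the other way for one group. No section says which takes precedence.

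Two things are at stake. One is safety handling: 8.6.1 provides no formal DSMB and leaves monitoring to the PI, so the written rule carries more weight than usual. The other is exposure: 7.3 defines the main population by attendance at the Day 60 visit, not by doses received, so a subject who received half the regimen counts the same as one who received all of it.

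**Working it through.** The point rests on comparing text. The plan gives no figure to reproduce.

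1. **When the conflict can matter.** Doses fall on Days 0, 1, 29 and 30 (5.2). For an event after dose 2 and before dose 3, the doses in question are 2 of 4, or 50% of the regimen. After Day 30 no drug remains to be withheld, so the conflict has no effect on dosing.

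2. **Medicine started on, say, Day 15.**
   - It can be safely held: the 4.2.4 criterion is arguably not met, 8.5 is not triggered, and there is no conflict.
   - It cannot be held: the criterion is met. Section 8.5 gives no doses 3 and 4. Sections 4.2.4 and 5.5 give a PI reassessment with the outcome open. Both apply to the same subject.
   - 4.2.4 refers to the Brochure generally and 5.5 to its Appendix 1. Whether these are the same list cannot be checked from the documents.

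3. **Steroid injection or wrist surgery on, say, Day 15.** On Day 29 the procedure is 29 − 15 = 14 days old, well within 6 months, so the 4.2.1 criterion is met. Section 8.5 stops drug; 4.4.1 asks a subject who tolerates fisetin to continue. Taken literally, both cannot be followed.

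4. **Laboratory result at Day 29.** Section 4.2.2 holds 16 numeric limits: bilirubin, AST, ALT (3); haemoglobin, white cells low and high, platelets, neutrophils, lymphocytes (6); glucose, HbA1c (2); creatinine, cystatin C, eGFR (3); CRP, ESR (2).
   - The haematology bullet contains a restriction to screening. It may govern the lymphocyte limit alone or all 6.
   - The glucose limit is for a fasting sample, and the safety panel in 6.9.7 does not specify fasting.
   - Limits that carry over to Day 29 without either qualification: 16 − 1 − 1 = 14, or 16 − 6 − 1 = 9.
   - All 16 sit under a lead-in that allows clinical judgement.
   - A CRP of 11 exceeds the limit of 10, yet a reviewer could call it not clinically significant. Section 6.4 does not say how that judgement relates to the limit, or what follows from a failed review. The abnormal-laboratory text in 8.1 lists follow-up actions but no dosing consequence.

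5. **Effect on the analysis set.** The subject in step 2 who cannot hold the medicine could end up in three ways:
   - kept on drug by the PI: 4 doses, in the main population;
   - stopped under 8.5 but still attending Day 60: 2 doses, in the main population;
   - participation ended by the PI: no further research data (4.4.2), replaced (4.4.1), not in the main population.

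   Each such subject is 1/40 = 2.5% of the planned number. Subjects in step 3 are already removed from the final analysis by 4.4.1, so for them the matter is safety and exposure only.

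**The case against.** The strongest reply is that a specific provision overrides a general one. Sections 4.2.4 and 5.5 could be the particular rule for new medicines, with the PI's reassessment being the step that decides whether the medicine can be held; 4.4.1 could likewise be the particular rule for added CTS treatment. The reassessment also concerns participation, whereas 8.5 concerns drug. Part of this stands: where the medicine can be held, nothing conflicts. But 8.5 covers any exclusion criterion and names no exception, and no section ranks the others above it. Section 4.4.1 shows that the protocol separates drug from other treatment and follow-up when it means to; 4.2.4 and 5.5 do not.

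On the laboratory side the reply is stronger. A reader might infer that 6.4 replaces the exclusion limits with a judgement of clinical significance. It does not: 6.4 and Table 1 also re-check eligibility at Day 29, which agrees with 8.5. A reader might also infer that crossing any of the 16 limits ends dosing automatically. The restriction to screening, the fasting condition and the clinical-judgement lead-in all tell against that. Nor is it a contradiction that a large ALT rise below 4 times the upper limit could be held under 6.4 but not under 8.5: a mandatory stop plus a further clinical check is an ordinary layered safeguard.

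Finally, the trial is single-site, which limits variation between readers, and much of the recording already exists (5.4, 3.7, 9.3). Both are fair and reduce the cost of the defect and of its repair. They do not settle which rule governs.

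**Conclusion.** The concern holds in limited form. Section 8.5 conflicts with 4.2.4 and 5.5 for a listed medicine that is started before the last dose and cannot be safely held. It conflicts with 4.4.1, more plainly, for a steroid injection or wrist surgery before the last dose. The Day 29 laboratory review is an ambiguity, not a contradiction.

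For an affected subject, up to 2 of 4 doses turn on which section is followed. How many subjects that is cannot be derived: the documents give no rate for new listed medicines, added CTS treatment or laboratory values past a limit, and any percentage would be a guess. The textual conflict does not depend on one. The conclusion assumes that 8.5 means what it says in covering all exclusion criteria, and that the Brochure, which is not among the documents, does not itself settle the order of precedence. The documents do not support a claim that every subject who meets an exclusion criterion faces contradictory rules.

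**What to change.** Reconcile 4.2.1, 4.2.2, 4.2.4, 4.4.1, 5.5, 6.4 and 8.5 into one Day 29 re-dosing rule, and refer to it from each section. For each exclusion criterion, the rule should say whether meeting it after enrolment is an automatic stop or a PI decision. For the laboratory limits, it should also say which apply at Day 29 and how the 6.4 review relates to them. State whether a subject who stops drug stays in follow-up, and use one reference for the Brochure's medicine list. Which rule applies to which criterion is for the sponsor and IRB to decide.

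Record in the CRF the criterion met and whether doses 3 and 4 were given, and report the number of subjects who received both cycles alongside the primary result.

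The cost is amendment wording and about one CRF item, since dosing is already documented in the chart and Drug Diary. No new test is needed, unless the fasting glucose limit is kept for Day 29, in which case the sampling condition must be stated.
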